## **Sponsor/Quotient Sciences Confidential**

---

If required, a PK analysis subset(s) will also be documented by Quotient, with approval from MMV, at the same time as the PK population and analysis set, if additional subjects are required to be excluded from the statistical analysis (i.e., to exclude subjects who have not received both the fed and fasted treatments in Part 2).

All enrolled subjects will be used for the PK data listings. The PK population will be used for the populations table. The PK analysis set and/or the PK analysis subset(s), if defined, will be used for the provision of PK summary tables and figures as well as the formal statistical analysis and will be documented as the same time as the PK population.

## **7 Participant Disposition, Demographics and Baseline Characteristics**

No formal statistical testing will be performed on participant disposition, or on demographic or baseline data. Summaries of participant disposition and analyses populations will be based on all enrolled subjects and summaries of all other data described in this section will be based on the safety analysis set unless otherwise stated.

### **7.1 Screening Failures**

For each study part, data for subjects who have failed screening will be databased but will not be cleaned and therefore will not be included in the SDTM or ADaM datasets or any of the TFLs or the CSR.

### **7.2 Participant Disposition and Withdrawals**

For each study part, the number and percentage of subjects randomised, dosed, completed and discontinued will be presented by sequence and overall in Part 2, and by all placebo, all active and each dose level in Part 1 and Part 3. If any subjects discontinued from the study early then the number of subjects for each reason for discontinuation will be presented by sequence and overall in Part 2, and by all placebo, all active and each dose level in Part 1 and Part 3. However, if none of the subjects are discontinued from the study early, then the reasons for discontinuation will not be populated in the summary table. A participant may be discontinued from the study early for 1 reason only.

Participant disposition and withdrawal data will be listed including details of informed consent.

Protocol deviations and any violations of the inclusion/exclusion criteria will also be listed.

### **7.3 Analysis Populations**

A summary table will be produced detailing the number and percentage of subjects in each population (i.e., safety/taste/PK, as applicable) by sequence and overall in Part 2, and by all placebo, all active and each dose level in Part 1 and Part 3. The reasons for exclusion from each population will also be included in the summary table. However, if none of the subjects were excluded from a population, then the reasons for exclusion will not be populated in the summary table. A participant may be excluded from a population for more than 1 reason. The denominator for the percentage is the number of subjects enrolled in the respective sequence in Part 2, and the number of subjects enrolled in Part 1 and Part 3.

Details of subjects included and excluded in the different analysis populations will be listed.

---

**Sponsor/Quotient Sciences Confidential**

---

**7.4 Analysis Sets and Subsets**

A summary table will be produced detailing the number and percentage of subjects in each of the safety, taste and PK analysis sets and analysis subsets (if applicable) for each treatment and overall in Part 2, and by all placebo, all active and each dose level in Part 1 and Part 3. Separate tables will be presented for safety, taste and PK, analysis sets and each table will be based on the relevant population the analysis set is derived from. If analysis subsets are defined they will be included on the same table as the corresponding analysis set. The reasons for exclusion from each analysis set/subset will also be included in the summary. However, if none of the subjects were excluded from an analysis set, then the reasons for exclusion will not be populated in the summary table. A participant may be excluded from an analysis set for more than 1 reason. The denominator for the percentage is the number of subjects in each population.

Details of subjects included and excluded in the different analysis sets/subsets will be listed.

**7.5 Demographic Characteristics and Lifestyle Details**

Demographic data (age, ethnicity, race, sex, height [cm], weight [kg] and body mass index [BMI; kg/m^2]) will be recorded at screening.

Summary statistics (number of subjects with an observation [n], mean, standard deviation [SD], median, minimum and maximum) will be presented for age, height, weight and BMI at screening by sequence and overall in Part 2, and by all placebo, all active and each dose level in Part 1 and Part 3. The number and percentage of subjects will be presented by sequence and overall in Part 2, and by all placebo, all active and each dose level in Part 1 and Part 3 for ethnicity, race and sex. The denominator for the percentage is all subjects in the safety analysis set. If any values are missing, a "missing" row will be presented on the table.

Lifestyle details (i.e., smoking history [does the participant smoke, use e-cigarettes or use nicotine replacement products?] and alcohol consumption) will be summarised by sequence and overall in Part 2, and by all placebo, all active and each dose level in Part 1 and Part 3, as a categorical variable.

Demographic and lifestyle data for all enrolled subjects will be listed. For Part 2 only, separate columns will be provided in the demographic listing for body weight at screening and admission.

**7.6 Medical History**

Medical history will be recorded for each participant at the screening visit and updated at admission. Medical histories will be coded using MedDRA v25.0 (or a more recent version) including Lowest Level Term, Preferred Term (PT), and System Organ Class (SOC).

All medical history data will be listed including coded terms.

**7.7 Prior and Concomitant Medication**

Medications (product name) will be coded using the World Health Organization (WHO) Drug Dictionary Global Drug Reference version 2022 March (or more recent version) using the following Anatomical Therapeutic Chemical (ATC) classification codes

**Sponsor/Quotient Sciences Confidential**

---

- Product name
- Preferred name
- Drug code
- Therapeutic subgroup (ATC 2nd level code)
- Chemical subgroup (ATC 4th level code)

Prior medications are defined as medications that start and stop prior to the first dose of IMP. All other medications will be defined as concomitant medications including those that start prior to the first dose of IMP and continue thereafter. Any medications with an unknown start or stop date will be assumed to be concomitant medications unless a partial start or stop date indicates otherwise.

All medications, including coded terms, and the underlying indication for which the medication was given, will be listed. One combined data listing of prior and concomitant medications will be provided. All prior medications as defined above will be flagged with a "#" symbol. Within this flagged group medications that started after screening and stopped before dosing of IMP will also be flagged using a "\*" symbol.

## **7.8 Other Baseline Characteristics**

All other baseline characteristics, as listed below, at screening and on admission (unless otherwise stated) will be listed separately for each study part:

- Carbon monoxide breath test
- Urine drug screen
- Alcohol breath test
- Severe acute respiratory syndrome coronavirus 2 (SARS-CoV-2) Antigen test
- Beck Depression Inventory (BDI-II) Questionnaire
- Virology (Screening only)
- Creatinine clearance (Admission only)
- Follicle stimulating hormone for female subjects (Screening only)
- Serum pregnancy test for female subjects (Screening only)
- Urine pregnancy test (Admission only)

## **8 Efficacy**

Not applicable for this Phase I study.

## **9 Pharmacokinetics**

### **9.1 Plasma PK Parameter Estimation**

The PK parameters ([Table 5](#) [Part 1 and 2], [Table 6](#) [Part 3]) for MMV367 in plasma will be estimated where possible and appropriate for each participant profile (i.e., treatment/day [where relevant]) by non-compartmental analysis methods using Phoenix WinNonlin software (v8.3 or a more recent version, Certara USA, Inc., USA). Additional parameters may be calculated if required, depending on the data.

#### **9.1.1 Definition of Plasma PK Parameters**

Plasma PK parameter definitions are provided in [Table 5](#) and [Table 6](#).

**Table 5 Plasma PK Parameter Definitions and Rounding Specifications – Part 1 and 2**

**Sponsor/Quotient Sciences Confidential**

Parameter	Definition	Unit	DP or SF	No. of DP/SF
Tmax	Time of maximum observed concentration	h	DP	2
Cmax	Maximum observed concentration	mass unit/mL	SF	3
AUC(0-24)	Area under the curve from time 0 to 24 h post dose	mass unit.h/mL	SF	3
AUC(0-48)	Area under the curve from time 0 to 48 h post dose	mass unit.h/mL	SF	3
AUC(0-72)	Area under the curve from time 0 to 72 h post dose	mass unit.h/mL	SF	3
AUC(0-last)	Area under the curve from time 0 to the time of last measurable concentration	mass unit.h/mL	SF	3
AUC(0-inf)	Area under the curve from time 0 extrapolated to infinity	mass unit.h/mL	SF	3
AUCextrap	Area under the curve (AUC) from time of the last measurable concentration to infinity as a percentage of the area under the curve extrapolated to infinity	%	DP	2
T1/2	Terminal elimination half-life	h	DP	2
lambda-z	First order rate constant associated with the terminal (log-linear) portion of the curve	1/h	DP	4
CL/F	Total apparent body clearance calculated after a single extravascular administration where F (fraction of dose bioavailable) is unknown.	mL/min	SF	3
CL a	Renal clearance calculated using plasma AUC – Part 1 only	mL/min	SF	3
Vz/F	Apparent volume of distribution based on the terminal phase calculated using AUC(0-inf) after a single extravascular administration where F (fraction of dose bioavailable) is unknown	L	SF	3
Frel Cmax	Relative bioavailability based on Cmax (Part 2 fed dosing only)	%	DP	2
Frel AUC(0-last)	Relative bioavailability based on AUC(0-last) (Part 2 fed dosing only)	%	DP	2
Frel AUC(0-inf)	Relative bioavailability based on AUC(0-inf) (Part 2 fed dosing only)	%	DP	2
lambda-z lower*	Lower limit on time for values to be included in the calculation of lambda-z	h	DP	2
lambda-z upper*	Upper limit on time for values to be included in the calculation of lambda-z	h	DP	2

DP: decimal places; NA: not applicable; SF: significant figures

\* these values should be listed but omitted from the descriptive statistics

a Renal clearance will only be calculated in Part 1 should a validated method be developed, and the urine concentrations be required to be reported by Quotient, as an addendum to the CSR**Table 6 Plasma PK Parameter Definitions and Rounding Specifications – Part 3**

**Sponsor/Quotient Sciences Confidential**

Parameter	Definition	Unit	DP or SF	No. of DP/SF
Tmax	Time of maximum observed concentration	h	DP	2
Cmax	Maximum observed concentration	mass unit/mL	SF	3
AUC(0-tau)	Area under the curve for the defined interval between doses (tau)	mass unit.h/mL	SF	3
T1/2	Terminal elimination half-life (Day 3 only)	h	DP	2
lambda-z	First order rate constant associated with the terminal (log-linear) portion of the curve (Day 3 only)	1/h	DP	4
CL/Ftau	Total body clearance calculated using AUC(0-tau) after repeated extravascular administration, where F (fraction of dose bioavailable) is unknown (Day 3 only)	mL/min	SF	3
Vz/Ftau	Apparent volume of distribution based on the terminal phase calculated using AUC(0-tau) after extravascular administration where F (fraction of dose bioavailable) is unknown (Day 3 only)	L	SF	3
AR Cmax	Accumulation ratio based on Cmax repeated dose/Cmax single dose (Day 3 only)	NA	DP	2
AR AUC	Accumulation ratio based on AUC(0-tau) repeated dose/AUC(0-tau) single dose (Day 3 only)	NA	DP	2
lambda-z lower*	Lower limit on time for values to be included in the calculation of lambda-z (Day 3 only)	h	DP	2
lambda-z upper*	Upper limit on time for values to be included in the calculation of lambda-z (Day 3 only)	h	DP	2

DP: decimal places; NA: not applicable; SF: significant figures

\* these values should be listed but omitted from the descriptive statistics

Dose will be used in the calculation of relevant PK parameters as per [Table 7](#).

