**5.3.1.2 Pharmacokinetics**

High oral bioavailability was observed in rats, and moderate oral bioavailability for mice and dogs. Minipigs showed a low bioavailability. Based on a physiological-based pharmacokinetic (PBPK) model, it has been predicted that MMV367 shows a high oral bioavailability, moderate volume of distribution and low blood clearance in humans, with a predicted human half-life of 19 h. Results from in vitro studies with human hepatocytes suggested that MMV367 is metabolised slowly in humans (predicted liver elimination of 1.60 mL/min/Kg). MMV367 has a low potential for drug-drug interactions based on in vitro findings. Results from a PK study in dogs suggested that concomitant food intake may increase systemic exposure to MMV367. Toxicokinetic data indicated that at high doses, elimination of MMV367 is limited by the solubility resulting in a prolonged apparent half-life.

Following intravenous administration of MMV367 to mice, rats dogs and minipigs, clearance values were low in mice and rats but high for dogs and minipigs. Associated mean terminal half-lives ranged between 0.6 h (dogs) and 2.1 h (mice).

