All approved standard of care treatments for acute uncomplicated malaria are administered for a maximum of 3 days duration. Therefore, in this study, MMV367 will be administered QD (morning dose) for a maximum of 3 days in Part 3. Considering its anticipated half-life of approximately 19 h, steady-state concentrations will not be achieved with a 3-day regimen. Although the pharmacological profile and PK properties of MMV367 are both expected to provide a single dose cure for acute uncomplicated malaria, the evaluation of a 3-day regimen will allow the assessment of tolerability and safety for an alternative therapeutic strategy in the target population. The assessment of up to a 3-day treatment regimen may be useful if a disconnect is observed in the predicted efficacy of the malaria human challenge model or malaria patients, such that MMV367 needs to be administered over 2 or 3 days to ensure a cure. Additionally, MMV367 will ultimately be administered/deployed in a fixed dose-combination regimen with an existing or novel antimalarial drug and dosing frequency will have to take the pharmacology of any proposed partner drug into account.

This study may also identify the genetic factors that affect the PK of MMV367 in humans through exploratory pharmacogenetic sampling. Such analysis will be triggered after study completion if specific safety and/or PK observations suggest that a genetic polymorphism could potentially account for variability in the study.

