Additionally, the findings in animal toxicological species were non-adverse, monitorable and reversible [\[3\]](#). Therefore, these increments are considered safe. Nevertheless, available PK data will be reviewed after each cohort to confirm that the observed AUC is comparable to the AUC simulated using the PBPK model and dose adjustments will be made, if required, before proceeding to the next cohort to ensure that the mean group exposure of the subsequent cohort will not exceed the highest achievable human exposure (AUCCap) of 376  $\mu\text{g.h/mL}$  and/or the Cmaxcap of 23.8  $\mu\text{g/mL}$ .

Selecting mean group values for human AUC(0-inf)cap and Cmaxcap in this FIH is considered acceptable due to the nature of the preclinical observations (GI toxicity, increased blood pressure/heart rate and decreased respiratory function) in the two GLP toxicology and safety pharmacology studies. These toxicities are not associated with steep dose-response relationship and are monitorable in humans.

**Sponsor/Quotient Sciences Confidential****Table 2 Margins between the Clinical Doses Predicted Plasma AUC(0-inf) and Cmax, and the Exposure at NOAEL in the Most Sensitive Species (Dog)**

Proposed Dose (mg)	Prediction in Human based on PBPK model		Exposure multiple in dogs (NOAEL dose 300 mg/kg QD for 7 days)		
	Cmax (µg/mL)	AUC(0-inf) (µg.h/mL)	Cmax (23.8 µg/mL) a	AUC(0-168) (1250 µg.h/mL) Cumulative method b,c	AUCtau(24h)-ss (192 µg.h/mL) Standard method d
Single dose					
100 mg	0.7	18.8	34.0	66.5	10.2
300 mg	2.2	55.5	10.8	22.5	3.5
750 mg	5.0	127	4.8	9.8	1.5
1500 mg	7.7	193	3.1	6.5	1.0
2000 mg	8.2	208	2.9	6.0	0.9 c
Multiple dose					
200 mg QD × 3	2.2	112	10.8	11.2	1.7

a Cmax after last dose in dogsb Cumulative exposure method, AUC(0-168) / predicted AUC(0-inf) in humans. The average cumulative AUC(0-168) is calculated as follows: (AUCD1 + AUCD7) / 2\*7.c The approach calculating safety margin based on the cumulative method is considered more relevant in our setting because the steady-state will never be reached due to the maximum 3-day QD treatment duration with a 19 h half-life.d Standard method: AUCtau(24h)-ss / predicted AUC(0-inf) in humansNote: AUCcap = 376 µg.h/mL, calculated exposure at 2000 mg assuming dose linearity from 100 to 2000 mg.

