**Sponsor/Quotient Sciences Confidential**

---

- Interim PK parameter estimations (Tmax, Cmax, AUC(0-24), AUC(0-48), AUC(0-last), AUC(0-inf), T1/2, where possible and appropriate)

Rules for dose decision are as follows:

- Dose increments between SAD cohorts will be a maximum of 3-fold and dose escalation may be halted in the SAD cohorts if an exposure plateau appears to have been reached
- Dose increments between multiple dose optional cohorts will be no more than 3-fold
- No dose selected for SAD or MAD will be expected to result in a mean group exposure at the next dose level (based on predicted human PK and assuming dose-linearity) greater than AUC(0-inf) 376 µg.h/mL, and Cmax 23.8 µg/mL based on the NOAEL in dogs and the corresponding human therapeutic exposure
- The predicted exposure (AUC(0-inf)) of the cumulative dose after a 3-day treatment will not exceed that of a single dose evaluated in Part 1
- The study will be halted (see [Section 8.5](#)) and thus a further dose decision will not be made if:
  - One or more participants experience an IMP-related serious adverse event (SAE)
  - Two or more participants experience an IMP-related severe or clinically significant non-serious AE at the same dose level/same cohort

If, following review by the SAC it is deemed acceptable to continue dose escalation above the defined maximal dose or exposure limit, a substantial amendment with relevant data will be submitted for approval to the Medicines and Healthcare products Regulatory Agency (MHRA) and ethics committee (EC).

*Progression from Part 1 (SAD) to Part 2 (Food Effect).*

For the dose level decision to be made for Part 2, data must be available from a minimum of 6 participants who have completed the planned safety assessments up to 7 days after dosing and planned PK assessments up to 144 h after dosing (to ensure at least 4 participants had received active IMP), at a relevant dose level in Part 1. A “relevant dose level” is defined as a dose that demonstrated acceptable safety/tolerability (i.e. exposure levels at which no study specific criteria stopping dose progression and/or escalation were met) at a mean exposure that is not anticipated to be exceeded by the dosing regimen in Part 2, taking into account a potential bioavailability increase to 100% after a high-fat breakfast.

*Progression from Part 1 (SAD) to Part 3 (Multiple Dose).*

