**Table 8 Plasma Pharmacokinetic Parameters: Part 3**

Parameter	Definition
Tmax	Time of maximum observed concentration
Cmax	Maximum observed concentration
AUC(0-tau)	Area under the curve for the defined interval between doses (tau)
T1/2	Terminal elimination half-life (Day 3 only)
CL/Ftau	Total body clearance calculated using AUC(0-tau) after repeated extravascular administration where F (fraction of dose bioavailable) is unknown (Day 3 only)
Vz/Ftau	Apparent volume of distribution based on the terminal phase calculated using AUC(0-tau) after repeated extravascular administration where F (fraction of dose bioavailable) is unknown (Day 3 only)
AR Cmax	Accumulation ratio based on Cmax repeated dose/Cmax single dose (Day 3 only)
AR AUC	Accumulation ratio based on AUC(0 tau) repeated dose/AUC(0 tau) single dose (Day 3 only)

Analysis of drug related QT/QTc interval changes relative to plasma PK concentrations will be conducted. This analysis will be performed on the analysis set for intensive cardiac assessment. Concentration/QTc modelling may be performed after completion of the CSR and will be reported separately.

In Part 1 Cohorts 1C and 1D, provided a future bioanalytical method is available, urine concentration data for MMV367, provided by Swiss BioQuant, will be analysed by Quotient and reported in an addendum to the CSR or in a separate report. Estimates of the parameters presented in [Table 9](#) in urine will be obtained where possible and appropriate.

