## **9.7 Interim Pharmacokinetic Analysis**

The details of the planned interim PK analysis are described in this section. However, as the analysis will be performed in real time it may be necessary to change the planned analysis in response to the emerging data.

Summary tables and figures for the interim PK analysis will be presented in an Interim PK Summary Report after being exported from WinNonlin. The formatting of this output will differ slightly from the final PK output which will be produced using SAS to include in the CSR.

The interim PK analysis will be performed on QC checked concentration data for MMV367 in plasma using nominal sampling times and doses. Measures will be taken to maintain the study blind according to [Section 5.7](#).

The following PK parameters will be calculated for the interim analysis:

Part 1:

Tmax, Cmax, AUC(0-24), AUC(0-48), AUC(0-last), AUC(0-inf), T1/2.

Part 3 Day 1:

Tmax, Cmax, AUC(0-tau)

Part 3 Day 3:

Tmax, Cmax, AUC(0-tau), T1/2, AR Cmax, AR AUC

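### Part 3 derives CL/Ftau and Vz/Ftau from a Day 3 AUC(0-tau) that is not at steady state (about 8% too high at a 19 h half-life), and pre-specifies no observed cumulative AUC(0-inf)

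*SAP*

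**What the plan says.** **Steady state.** Protocol 5.3.1.2 describes MMV367 "with a predicted human half-life of 19 h". Protocol 6.1 concludes that "steady-state concentrations will not be achieved with a 3-day regimen". Protocol 6.2 repeats the point, and footnote c of Protocol Table 2 prefers the cumulative safety margin "because the steady-state will never be reached due to the maximum 3-day QD treatment duration with a 19 h half-life".

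**Part 3 clearance and volume.** SAP Table 6 defines CL/Ftau as "Total body clearance calculated using AUC(0-tau) after repeated extravascular administration, where F (fraction of dose bioavailable) is unknown (Day 3 only". Protocol Table 8 has the same definition, and both tables define Vz/Ftau from AUC(0-tau) as well. Neither table adds a steady-state condition, and none of the flags in SAP Table 9 covers it.

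**Dose rules.** Protocol 8.2.2 states: "The predicted exposure (AUC(0-inf)) of the cumulative dose after a 3-day treatment will not exceed that of a single dose evaluated in Part 1". It also limits the expected mean group AUC(0-inf) to 376 µg.h/mL for single and multiple dosing. Protocol 6.2 says that PK will be reviewed after each cohort to confirm that the observed AUC is in line with the simulated one. Table 2 in that section gives a simulated cumulative AUC(0-inf) for Part 3: 112 µg.h/mL for 200 mg QD × 3.

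**Part 3 parameter lists.** For Day 3, the interim list in SAP 9.7 is "Tmax, Cmax, AUC(0-tau), T1/2, AR Cmax, AR AUC". The final list in SAP 9.1.3 adds lambda-z and its limits, CL/Ftau and Vz/Ftau. Day 1 has Tmax, Cmax and AUC(0-tau) in both lists. AUC(0-last), AUC(0-inf) and a cumulative AUC appear in neither.

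**The concern.** Before steady state, the AUC over a dosing interval is smaller than the single-dose AUC(0-inf), so dose divided by it overstates clearance. Vz/Ftau inherits the same factor through lambda-z. CL/F and Vz/F are among the named secondary PK endpoints. Part 1 defines Vz/F from AUC(0-inf), so the two parts would report quantities that look alike but are built differently.

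The second matter is the exposure check. The protocol sets its Part 3 exposure limits on the AUC(0-inf) of the whole course and simulates that quantity. The pre-specified outputs give the committee no observed counterpart to set beside the simulation when it considers Cohorts 3B and 3C after Cohort 3A.

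**Working it through.** **Inputs.** Half-life 19 h (Protocol 5.3.1.2), so k = ln 2/19 = 0.0365 /h. Three doses, tau 24 h (Protocol 8.1.3). Predicted AUC(0-inf): 18.8 µg.h/mL at 100 mg, 55.5 at 300 mg, 112 for 200 mg QD × 3 (Protocol Table 2). The documents write no formula for the tau parameters, so the standard ones are assumed: CL/Ftau = dose/AUC(0-tau) and Vz/Ftau = dose/(lambda-z × AUC(0-tau)).

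**1. The plan's own figure.** By superposition, cumulative AUC(0-inf) for 200 mg × 3 is 3 × 2 × 18.8 = 112.8 from the 100 mg row, or 2 × 55.5 = 111.0 from the 300 mg row. Table 2 gives 112 and a margin of 1250/112 = 11.2, so it reproduces. The text of Protocol 6.2 gives 114 for the same quantity; the two should be aligned.

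**2. Share of steady state on Day 3.** The Day 3 interval contains hours 0–24 of dose 3, 24–48 of dose 2 and 48–72 of dose 1. Under linear, time-invariant PK its AUC therefore equals single-dose AUC(0-72), while the steady-state value equals AUC(0-inf).
- Bolus input: 1 − 2^(−72/19) = 0.928.
- First-order absorption: 1 − [ka·exp(−72k) − k·exp(−72ka)]/(ka − k). This gives 0.925 at ka = 1.0 /h and 0.918 at ka = 0.3 /h (both ka values assumed).

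**3. Bias = 1/share − 1.**
- At 19 h: 7.8% (bolus), 8.1% (ka 1.0), 9.0% (ka 0.3). With the linear-log trapezoid on the scheduled Part 3 samples: 8.3% (ka 1.0) and 9.5% (ka 0.3).
- At other half-lives, all assumed, bolus input: 12 h 1.6%; 24 h 14.3%; 30 h 23.4%; 48 h 54.7%.

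**4. In the plan's units.** From Table 2, CL/F = 600/112 = 5.36 L/h (89 mL/min). The Day 3 formula gives 5.36/0.928 = 5.77 L/h (96 mL/min).

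**5. What the listed AUCs cover.** Day 1 AUC(0-tau) is 1 − 2^(−24/19) = 0.583 of single-dose AUC(0-inf), and Day 3 is 0.928. Together they hold (0.583 + 0.928)/3 = 50% of the cumulative AUC(0-inf).

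**6. Whether the schedule supports the missing parameter.** The same simulation, using scheduled samples from first dose to 144 h after the third plus extrapolation, recovers 98.6 to 99.1% of the true cumulative AUC(0-inf) at 19 h. The extrapolated part is 0.3% at 19 h, about 2.5% at an assumed 30 h and about 10% at an assumed 48 h. All are below the 20% exclusion limit in SAP 9.1.3.

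**The case against.** The case for leaving the plan alone has several good parts.

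- **The bias is modest.** The only human half-life in the documents is 19 h, which gives about 8%. The prolonged half-life in Protocol 5.3.1.2 is a toxicokinetic finding at high doses, with no human value attached. This stands: larger biases are conditional on a half-life that the documents do not give.
- **Part 3 need not look higher than Part 1.** A reader might infer that Part 3 clearance will exceed Part 1 throughout and be mistaken for induction. Table 2 does not support that. Dose/AUC(0-inf) is 100/18.8 = 5.32, 300/55.5 = 5.41, 750/127 = 5.91, 1500/193 = 7.77 and 2000/208 = 9.62 L/h. The Part 3 value of 5.77 lies above the two lowest doses and below the other three. No comparison of clearance between parts is planned, and the parameter names differ.
- **The rules cap a prediction.** A reader might infer that the committee would have no estimate of the capped quantity. The wording of Protocol 8.2.2 concerns predicted exposure, which can be projected from Part 1 AUC(0-inf), as step 1 shows. Cmax, AUC(0-tau), T1/2 and the accumulation ratios would also give some warning of a departure.
- **The SAP leaves room.** SAP 9.1 permits additional parameters, and SAP 9.7 permits the interim analysis to change with the data. So the parameter is not pre-specified, rather than ruled out.

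Two things remain. The permissive clauses name no parameter, whereas Protocol 6.2 makes a definite undertaking about observed against simulated AUC. Also, projection from Part 1 rests on proportionality, and Table 2 predicts that this weakens: AUC per mg is 112/600 = 0.187 for the split regimen, against 127/750 = 0.169 and 193/1500 = 0.129 for larger single doses. A limit on total dose is therefore not by itself a limit on exposure, and an observed value is the direct check.

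**Conclusion.** The point holds at moderate size and should be fixed. CL/Ftau and Vz/Ftau contradict the protocol's own statement about steady state. Both are biased upward by about 8% at the 19 h half-life, or 8 to 9.5% with assumed absorption rates. The direction and size rest on linear, time-invariant PK. The bias would reach about 23% only if the half-life were 30 h, which is an assumption.

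No observed cumulative AUC(0-inf) is pre-specified for Part 3, final or interim, although its predicted value is capped and an observed-to-simulated comparison is promised.

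AR Cmax and AR AUC are unaffected as Day 3/Day 1 ratios, provided that they are not read as steady-state accumulation. The planned Part 3 dose-proportionality analysis of Cmax and AUC(0-tau) and the primary safety objective are also untouched.

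**What to change.** This changes the analysis only; dosing and sampling stay as they are. In Protocol Table 8 and SAP Table 6, 9.1.3 and 9.7:

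- Add AUC(0-last) and AUC(0-inf) for the whole course, treating the three doses as one profile from the first dose to 144 h after the third, plus extrapolation.
- Derive CL/F = total 3-day dose/cumulative AUC(0-inf), and Vz/F = (CL/F)/lambda-z.
- Drop CL/Ftau and Vz/Ftau, or label them 'not at steady state'.
- Put cumulative AUC(0-inf) in the interim report to the safety advisory committee, beside the simulated value.

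As a cross-check, Part 1 AUC(0-72)/AUC(0-inf) estimates the Day 3 shortfall directly. AUC(0-72) is defined in SAP Table 5 but missing from the reporting list in 9.1.3.

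The cost is table wording and one extra non-compartmental run on samples already scheduled. There is one small downside: Day 2 has no samples between pre-dose and 4 h, so that stretch is interpolated. In the simulation at 19 h the cumulative AUC came out 0.9 to 1.4% low, a smaller error than the one removed.
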